- · The proposed sample composition of subjects.

You may reference grant application/sponsor's relevant protocol pages and attach as an appendix using the below attachment button, however, a summary paragraph must be provided in the text box below.

Proposed dates of enrollment: November 1st, 2020 to December 31st, 2021

The trial will be conducted in Iquitos, Peru. Patients will be recruited from the community, local health-care clinics, and post-secondary educational institutions through word-of-mouth, active recruitment by study staff, and self-referral in response to advertisements. Verbal permission will be sought at private locations where advertisements will be posted, and a signed letter of authorization will be obtained from any performance site where recruitment activities take place. Men and women between the ages of 18 and 70 years with P. falciparum or P. vivax malaria monoinfection living in Peru. 2-6 cohorts of adult patients (10 patients per cohort) with acute,

53333

uncomplicated P. falciparum or P. vivax malaria monoinfection. In total, there will be a minimum of 20 and a maximum of 60 patients. In general, the people who live in these recruitment areas are representative of the general population that suffers malaria in the Amazon region. They are generally mestizo and do not live in extreme poverty. Their educational level includes completion of primary or high school.

Inclusion Criteria:

1) Male or female, aged 18 to 70 years of age (inclusive) at screening.

2) Body weight between 45 kg and 90 kg inclusive

3) Presence of mono-infection of P. falciparum or P. vivax confirmed by:

a. Fever, as defined by axillary temperature = 37.5°C or oral/rectal/tympanic temperature = 38°C, or history of fever in the previous 24 hours (history of fever must be documented) and,

b. Microscopically confirmed parasite infection: 1,000 to 40,000 asexual parasite count/µL blood

4) Written informed consent provided by participant, in accordance with local practice. If the participant is unable to write, witnessed consent is permitted according to local ethical considerations.

5) Ability to swallow oral medication.

6) Ability and willingness to participate and to comply with the study requirements

7) Agreement to hospitalization for at least 102 hours and/or until malarial parasites are not detected by microscopy on 2 consecutive occasions.

8) Agreement to come back to the hospital on Days 7, 10 or 11, 14, 17 or 18, 21, 24 or 25, 28, 35, and 42.

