Cohort 2 will test whether pharmacoenhancement of SJ733 with cobicistat is required for clinical efficacy. If cohort 2 meets the success criteria, the trial will be complete. If data from cohort 2 are inconclusive, an adaptation will be triggered to use the same regimen for a larger number of patients in order to improve statistical power and more accurately classify a potential failure. If cohort 2 proves safe (no repeated drug-related SAE) but not efficacious (crude ACPR < 60%), an adaptation will be triggered to use an intermediate exposure of SJ733, obtained by pharmacoenhancement of a reduced dose of SJ733 (optional cohort 3). Due to the pharmacoenhancing effects of cobicistat, a co-dose of SJ733 (300 mg) + cobicistat (150 mg) is expected to yield a higher total plasma exposure (median AUC) of SJ733 than a dose of SJ733 (600 mg) alone (Figure 1). The increase in plasma exposure is expected to provide increased efficacy. While cohort 3 requires co-dosing with a pharmacoenhancer, if successful, this regimen would reduce the quantity of SJ733 required by two-fold, lowering cost of goods and potentially improving tolerability.

Cohorts 1a and 1b are expected to achieve roughly five-fold higher plasma exposure of (+)-SJ733 than Cohorts 2a and 2b. Thus, if Cohorts 1a and 1b prove efficacious but repeated drug-related adverse events are observed, the Investigator, DMC, and SRT may unanimously agree that no further patients should be recruited to Cohorts 1 but that patient recruitment to Cohorts 2 should still be pursued. In this scenario, the Investigator will assess the severity/intensity of the adverse reactions and clinical laboratory changes using the DMID Toxicity Grading Scale for Determining the Severity of Adverse Events provided in Protocol Attachment 3 and Section 8.1.2. This information will be relayed to the DMC and SRT, who will make recommendations regarding further conduct of the trial, and if considered necessary, may recommend pausing or stopping further administration of the investigational product. Cohort progression will only be explored if the Investigator, DMC, and SRT unanimously agree it is warranted and appropriate. These recommendations will also be communicated to the Ethics Committee and Regulatory Authority and any necessary updates will be made to the patient consent form.

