 - 24 hours after administration of study drug
 - 48 hours after administration of study drug
 - 72 hours after administration of study drug
- Proportion of microscopically determined parasitemia in patients at:
 - 24 hours after administration of study drug
 - 48 hours after administration of study drug
 - 72 hours after administration of study drug

Secondary endpoints related to PK parameters up to Day 42

AUC_{0-t}, AUC_{0-inf}, C_{max}, t_{max}, t_½, Cl, F, etc.

Exploratory Endpoints:

- PCR-adjusted ACPR at Days 7, 14, 28, 35, and 42 (*P. vivax* or *P. falciparum*)
- PCR determined recurrence (*P. vivax* or *P. falciparum*) up to Day 42
- Correlation between parasite genotypes of interest and parasite clearance kinetics/efficacy

Data Sources

Data will be entered into REDCap instruments per the Data Management Plan (DMP). Clinical, laboratory, and safety study measures will be entered into the electronic data capture system (REDCap) and assessed for quality as outlined in the DMP.

Creation of Analysis Datasets and Analytic Data Handling

Data from REDCap will be exported and converted to SAS datasets. Analysis datasets will be created, and SAS programs will be developed to further investigate potential data issues via simple descriptive statistics and plots. Summary reports will be provided periodically during the course of the project to verify accuracy of data entry and provide early opportunities for clarification of questions and correction of errors and omissions.

For analysis datasets, Data Definition Tables (DDTs) are included to document all variables (both raw and derived) included in the analysis datasets. This includes the variable name, label, type, length, format, coded values and logic for creating derived variables. For raw data, a data dictionary is available through REDCap. The data dictionary provides a description of all data fields including the field name, label, field type, response option coding and branching logic.

Quality assurance strategies outlined in the DMP will be used to minimize missing data. In general, primary analyses will be conducted as observed. In the event imputation is needed and appropriate, it will be employed using multiple imputation methods. In the presence of imputation, the sample size is not diminished. A description of participant disposition will be included to assess incomplete data, visits, withdrawals, deviations, and discontinuations.

4. Statistical Methods

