The overall study design is to demonstrate proof of concept and serves as an exploratory study. It is not intended to demonstrate superiority or non-inferiority against a control. Rather the goal is to establish preliminary data for planning future studies and to assess whether the SJ733 is safe and the observed curative rate equals or exceeds 80%. As such, there will be no statistical testing of hypotheses. This exploratory Proof of Concept study uses a fixed clinical safety and parasitological responses (primary endpoints) defined as the absence of any drug-related SAE or microscopically determined parasitemia 14-days after initiation of therapy in \geq 80% patients who did not violate any of the inclusion/exclusion criteria.

General Approach

The overall study design involves two cohorts receiving SJ733 doses (600 mg and 300 mg) with and without cobicistat (150 mg) as cohorts. Data subsets (eligible, evaluable and completer) will be used in the potential comparisons.

The primary analytic approaches will be descriptive. All data will be summarized descriptively for the appropriate analysis sets defined below: Continuous variables by descriptive statistics (number of patients [n], mean, standard deviation [SD], minimum, median, maximum); categorical data by absolute and relative frequencies (n and %) or contingency tables.

While this is a proof of concept, exploratory study, any potential comparisons between dose cohorts will be informative. Potential longitudinal data will be described as graphical summaries presented by each group. Unless indicated otherwise, summary statistics will be reported for observed data only, by dose cohort. Missing data will not be imputed. If a baseline value is missing, no change from baseline will be calculated.

Baseline is defined as the last observation prior to the administration of study medication.

SAS v9.4 or higher will be used for all analyses and a significance level of 0.05 will be used for all statistical tests.

Primary Analysis (Efficacy)

Primary analyses will be conducted across the two cohorts and by the two cohorts. Estimates will be presented with 95% confidence intervals.

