The primary efficacy endpoints will be summarized descriptively, across the two cohorts and by the two cohorts. A statistical test will not be performed on the Crude ACPR on Day 14. Achieving a rate of 80% will be the decision rule for cohort dose phase. For future study planning, a one-sample z-test will be used to compare the rate of success, as defined by the Crude ACPR on Day 14, to the hypothesized rate of 80%.

Secondary efficacy variables will be summarized descriptively (by cohort; on Days 0, 14, 42) with proportions, means, and medians. To inform future studies, all estimates will be presented with 95% confidence intervals ($1.96 \pm$ margin of error). Graphical summaries will be used to describe changes in efficacy endpoints over time.

Exploratory Analysis

Exploratory model-based analyses will be performed as data allows. These will include model-based analyses of PK, PD and PK/PD.

Safety Analysis

Adverse events (AEs) will be summarized in Listing 9: Cumulative Summary of Adverse Events. The listing will include the following information: Patient ID, AE Description, Start Date, Stop Date, Special Interest, Severity, Relationship to Study Drug, Action Taken, Outcome of AE, Expected AE, and if the AE was a Serious Adverse Event (SAE).

Laboratory values that fall outside a clinically accepted reference range must be evaluated and commented on by the Investigator and graded according to the DMID Toxicity Scale for Determining Severity of Adverse Events (Protocol Attachment 3, Section 8.1.2).

All related AEs, AEs with outcome death, AEs leading to permanent discontinuation of treatment, SAEs and related SAEs will be summarized in Listing 10: Cumulative Summary of Serious Adverse Events. The listing will include the following information: Patient ID, Age, Sex, Dose, SAE Description, Start Date, Stop Date, SAE Category, and Relationship to Study Drug.

Treatment related AEs are those rated by the Investigator as "definite", "probable", "possible". In case relationship is unknown or missing the worst case will be assumed and the AE will be considered to be drug related

Planned Interim Analyses

Interim analyses will be made to review parasite reduction, adverse events, and clinical laboratory data. Following review, a decision on cohort progression will be made. However, as this is an exploratory study no formal analyses with adjustments for type I error are planned.

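### AUC, Cmax and baseline parasite density need a log-scale summary and interval; the SAP gives one linear-scale rule for all continuous data and a 1.96-based interval (minor)

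*Combined protocol and SAP*

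**What the plan says.** SAP section 4, General Approach, applies one rule to everything: "All data will be summarized descriptively for the appropriate analysis sets defined below". Its list for continuous data is "Continuous variables by descriptive statistics (number of patients [n], mean, standard deviation [SD], minimum, median, maximum".

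SAP section 4, Primary Analysis (Efficacy), adds: "Secondary efficacy variables will be summarized descriptively (by cohort; on Days 0, 14, 42) with proportions, means, and medians". The next sentence in that paragraph promises 95% intervals for all estimates, to inform future studies, and builds them with 1.96. No other interval method for continuous data appears.

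SAP section 3 lists AUC and Cmax under "Secondary endpoints related to PK parameters up to Day 42" without a rule of their own. SAP section 5 lists no PK table, figure or listing.

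Exposure is discussed as a ratio or an ordering. SAP section 2 states "Cohorts 1a and 1b are expected to achieve roughly five-fold higher plasma exposure" relative to Cohorts 2a and 2b, and says that the Cohort 3 regimen "is expected to yield a higher total plasma exposure (median AUC) of SJ733" compared with the unboosted one. Eligible baseline density spans 40-fold (Study Population, inclusion criterion 3b): "Microscopically confirmed parasite infection: 1,000 to 40,000 asexual parasite count" per microlitre.

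**The concern.** AUC, Cmax and parasite density cannot be negative, usually have a long right tail, and are read as fold differences. For such data the arithmetic mean is pulled towards the highest patients, and a symmetric interval around it tends to cover less often than its label says in small samples. Groups here are small: 10 patients per parasite arm, 20 per dose when arms are pooled.

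At stake are the secondary PK and parasite-density summaries that Phase 2b planning will draw on. Exposure also has a part in this trial. The Benefit vs. Risk section of the IRB application names exposure up to Day 14 as one basis for the decision on the next cohort, and the Data and Safety Monitoring section has the safety review team look at PK data if available. Yet no estimate of the exposure ratio between cohorts, with an interval, is specified.

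**Working it through.** The plan has no figure on this point that can be recomputed: the five-fold exposure ratio is an expectation, and no AUC data or CVs are given. Every CV below is an assumption, as is the log-normal shape.

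**1. Coverage of the stated interval.** Inputs: n = 10 per arm and n = 20 per pooled dose (SAP section 4, Sample Size Justification); CV of 40%, 80% or 100% (assumed). The log-scale SD is σ = √ln(1 + CV²), which gives 0.385, 0.703 and 0.833. The SAP interval is read as mean ± 1.96 × SD/√n. Share of 200,000 simulated samples in which the interval contains the true value:

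| CV (assumed) | 1.96 interval, n = 10 | t interval, n = 10 | 1.96 interval, n = 20 | log-scale t interval, either n |
|---|---|---|---|---|
| 40% | 90% | 93% | 92% | 95% |
| 80% | 86% | 89% | 89 to 90% | 95% |
| 100% | 84% | 87% | 88% | 95% |

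The first three interval columns target the arithmetic mean and the last targets the geometric mean, which equals the median for log-normal data. Part of the shortfall is not due to skew: with exactly normal data and n = 10, the 1.96 interval covers P(|t₉| < 1.96) = 91.8%, so 95 − 91.8 = 3.2 points come from using z instead of t.

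**2. Ratio of exposures.** For log-normal data, arithmetic mean ÷ median = √(1 + CV²). If the true ratio of medians is 5, the ratio of arithmetic means tends to 5 × √[(1 + CV₁²)/(1 + CV₂²)], with 1 = boosted and 2 = unboosted.

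- Equal CVs: 5.00, no bias.
- 40% and 80%: 5 × √(1.16/1.64) = 4.21.
- 80% and 40%: 5 × √(1.64/1.16) = 5.95.
- Extremes if both CVs lie between 30% and 80%: 4.08 and 6.13, that is −18% and +23%.

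With equal CVs the gain in precision is also small. At n = 20 and CV 50%, the central 95% of simulated ratios is 3.67 to 6.82 for arithmetic means and 3.73 to 6.70 for geometric means.

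**3. Baseline parasite density.** If log-uniform on 1,000 to 40,000 (assumed), the arithmetic mean is 39,000/ln 40 = 10,572 and the geometric mean is √(1,000 × 40,000) = 6,325, a ratio of 1.67. In simulated arms of 10, the two highest patients typically carry about 49% of the sum (95% range 36% to 67%).

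**The case against.** The strongest reply is that the SAP already prints the median, minimum and maximum beside the mean. For log-normal data the median equals the geometric mean, so a reader can form an undistorted ratio without any change. This stands for point estimates. It does not supply an interval for the median or for a ratio.

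The 1.96 interval sits in the secondary-efficacy paragraph, so its use for AUC and Cmax is inferred from the wording about all estimates. That is a fair caution, but no alternative method is given. Model-based PK and PK/PD analyses are planned, though only as data allow, so they do not replace a defined secondary summary.

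Two stronger readings are tempting, and the documents support neither:

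- *That the summary rule distorts the exposure ratio behind the dose steps.* The five-fold figure was set before these data, the metric named for the Cohort 3 step is median AUC, and no ratio of arithmetic means is planned. The SAP's progression guideline counts cured patients and repeated drug-related serious adverse events, and its interim review does not list PK. The IRB application does name exposure, and the two passages should be reconciled, but it does not specify a mean ratio.
- *That a few patients will drive the parasite curves.* The SAP does not say that Figures 2a, 2b and 3 plot means, and states no axis scale. Several clearance endpoints are times or relative reductions, which high baseline counts do not dominate.

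**Conclusion.** The point holds as a minor, nearly free improvement. The SAP names no log-scale summary for quantities that call for one, and its only stated interval would probably cover less than 95%: about 84% to 90% at n = 10 and 88% to 92% at n = 20, under assumed log-normal CVs of 40% to 100%. Those figures combine skewness with the use of z for t. The possible error in an observed exposure ratio is conditional: zero at equal CVs, and between −18% and +23% at the extremes of an assumed 30% to 80% range. The parasite-density figures rest on an assumed log-uniform baseline.

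The primary endpoint and the SAP's progression guideline are unaffected, because both rest on counts of patients or events.

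**What to change.** In SAP section 4:

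- For AUC, Cmax and baseline parasite density, add the geometric mean, the geometric CV and a 95% interval computed on the log scale with t quantiles and back-transformed. Keep the median and range.
- Report exposure in Cohort 1 relative to Cohort 2, and in Cohort 3 relative to Cohort 2 if Cohort 3 is run, as a geometric mean ratio with a 95% interval. Add a PK output to section 5 to hold it.
- Do not use geometric means for serial parasite and qPCR counts. These reach zero, where a geometric mean is undefined. In Figures 2a, 2b and 3, show individual profiles or medians on a log axis, with undetectable values plotted at the detection limit.

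The cost is SAP wording, a change in summary code, slightly more output and a stated plotting value for undetectable counts. No new data are needed.

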or not tolerated, patients will receive standard treatment from the study physicians following the protocol for treating malaria according to current Peruvians standards (see Available Alternative Treatment).

Back to Top

Safety Precautions: Describe the procedures for protecting against or minimizing any potential risks, *including risks of breach of confidentiality or invasion of privacy*. Where appropriate, discuss provisions for ensuring necessary medical or professional intervention in the event of adverse events, or unanticipated problems involving subjects. Also, where appropriate, describe the provisions for monitoring the data collected to ensure the safety of subjects. If vulnerable populations other than adults with impaired consent capacity are to be recruited, describe additional safeguards for protecting the subjects' rights and welfare.

Established antimalarial therapy will be given if a patient meets any of the following criteria:

1) Clinical decline or lack of clinical improvement or decrease in platelets by > 20% for Patients with a platelet count at inclusion of between 50,000/mm3 and 74,999/mm3 (thrombocytopenia grade 2) or a drop in platelet count to < 50,000/mm3 for

Patients with a platelet count of > 75,000/mm3 at inclusion, at 24 hours for P. vivax malaria and 12 hours for P. falciparum malaria Patients with a = 25% increase in parasitemia in comparison to baseline with or without fever.

2) Development of any clinical complications (WHO definition of complicated/severe malaria, WHO [2013])

3) Parasitemia > 100,000/µL for P. falciparum at any time with or without fever

4) Parasitemia > baseline (from the slides taken 30 min before start of treatment) with or without fever, 48 hours after first dose for P. vivax and 36 hours after first dose for P. falciparum

5) Failure to clear all parasites by microscopy associated with axillary fever > 37.5°C between 72 hours and 7 days for P. vivax and 60 hours and 5 days for P. falciparum

6) Failure to clear all P. vivax parasites by microscopy with or without fever on Day 7 and P. falciparum parasites by microscopy with or without fever on Day 5

7) Patient exhibits a rise of microscopically detectable parasitemia between Day 7 and Day 42 with or without fever

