• Proportion of patients with a decrease in hemoglobin (Hb): > 2 g/dL from baseline to an absolute value of < 5 g/dL

- Proportion of patients with an absolute Neutrophil count $< 1,000/\mu$ L after baseline
- Proportion of patients meeting Hy's law criteria
- Proportion of patients with the following LFT changes:
 - Any ALT or $AST \ge 5 \times ULN$
 - Any AST or ALT ≥ 3 x ULN together with the appearance of fatigue, nausea, vomiting, right upper quadrant pain or tenderness, fever, rash and/or eosinophilia (eosinophil percent or count above the ULN)
 - Persistent ALT $\ge 3 \text{ x}$ ULN for a period of more than 4 weeks.

• Proportion of patients with clinical signs of possible cutaneous adverse reactions such as dermatitis, rash, erythematous rash, macular rash, papular rash, maculo-papular rash, pruritic rash, pustular rash, vesicular rash

• Proportion of patients with clinically significant increases in venous methemoglobin levels

• Proportion of patients with significant changes in ECG findings, including heart rate, ECG intervals (PR, QTcB, QTcF), conduction changes or abnormalities

Success criterion: No repeated drug-related serious adverse events (Attachment 3, Section 8.1.2).

Secondary Endpoints

Secondary endpoints related to malaria signs and symptoms up to Day 42

- Proportion of patients with symptoms or physical examination signs related to uncomplicated *P. vivax* or *P. falciparum* malaria (dizziness, headache, nausea, anorexia, vomiting, diarrhea, pruritus, urticaria, skin rash, abdominal pain, joint pain, muscle pain, palpitations, sleep disturbance, confusion, hearing disturbance, visual disturbance, fatigue)
- Fever Clearance Time as defined as the time from baseline to the first of two consecutive post-dose axillary temperature measurements < 37.5°C obtained within an interval of 4 to 24 hours of each other.

Secondary endpoints related to secondary treatment outcomes

- Crude ACPR at Days 28, 35, and 42 (*P. vivax* or *P. falciparum*)
- Recurrence (*P. vivax* or *P. falciparum*) up to Day 42

Secondary endpoints related to parasite clearance kinetics by microscopy

- Parasite clearance time (PCT)
- PRR (parasite reduction rate) and parasitemia half life
- Times to microscopic clearance of asexual parasites
 - Total reduction (PC100)
 - 99% reduction (PC99)
 - 90% reduction (PC90)
 - 50% reduction (PC50)
- Microscopically determined percentage reduction in asexual parasites from baseline at:

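### Parasite and fever clearance times are summarised as observed-only means and medians, with no rule for patients rescued before they clear, so clearance can look faster than it was

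*Combined protocol and SAP*

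**What the plan says.** SAP section 3 (Secondary Endpoints) has a block titled "Secondary endpoints related to parasite clearance kinetics by microscopy". It contains parasite clearance time and the times to 50%, 90%, 99% and total reduction. Fever clearance time appears just above, under malaria signs and symptoms.

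The only analysis stated for these variables is in SAP section 4, Primary Analysis (Efficacy): a descriptive summary by cohort, for Days 0, 14 and 42, "with proportions, means, and medians". The General Approach adds: "Unless indicated otherwise, summary statistics will be reported for observed data only, by dose cohort", followed by "Missing data will not be imputed". Section 3 (Creation of Analysis Datasets) points the other way: "In the event imputation is needed and appropriate, it will be employed using multiple imputation methods". Neither rule mentions rescue. The General Approach names eligible, evaluable and completer subsets, but the text supplied does not define them.

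Rescue is set out in the IRB application, Safety Precautions. Established therapy is given, among other triggers, for:
- parasitemia above baseline at 36 h (*P. falciparum*) or 48 h (*P. vivax*);
- "Failure to clear all parasites by microscopy associated with axillary fever", from 60 h to Day 5 (*P. falciparum*) or 72 h to Day 7 (*P. vivax*);
- parasites still present, with or without fever, on Day 5 (*P. falciparum*) or Day 7 (*P. vivax*).

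No censoring, competing-event or rescue rule is given for the clearance times. The planned outputs contain no table or figure of them. Fever clearance time and definitive antimalarial treatment appear only as Listings 4 and 8.

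**The concern.** A clearance time exists only for a patient who clears. A patient rescued first has no clearance time attributable to SJ733. Read literally, the plan leaves two ways to handle that patient:

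- **Leave the patient out, as not observed.** The parasite-based rescue triggers pick out slow responders, so the mean and median are taken over the faster patients.
- **Use the time at which parasites or fever disappeared after rescue.** The rescue drug's effect is then credited to SJ733.

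Both errors run towards faster clearance and grow with the share of patients rescued. Two cohorts with different rescue rates would be understated by different amounts, and a descriptive contrast between them would tend to shrink. The General Approach says that comparisons between dose cohorts will be informative, and the results are meant to help choose doses for Phase 2b.

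**Working it through.** **The plan's own figures.** The SAP states no figure for clearance times, rescue rates or their precision. Its one design calculation is the power of the Day 14 test: Φ{[(0.98 − 0.80) − 1.645·√(0.80·0.20/20)] / √(0.98·0.02/20)} = Φ(1.050) = 85.3%, in line with the stated minimum of 85%. It has no bearing on this point.

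**Assumptions.** Clearance times T are lognormal with median m and log-SD 0.5. Every patient uncleared at time c is rescued then and drops out of the observed summary. The values of m and the log-SD are assumed. The values of c come from the Safety Precautions section: 60 h and 72 h are the earliest times for rescue with fever, and 120 h and 168 h (Days 5 and 7) are the times for rescue regardless of fever.

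**Formulas.** With z = ln(c/m)/0.5 and F = Φ(z):
- share uncleared = 1 − F
- observed-only median = m·exp(0.5·Φ⁻¹(F/2))
- true mean = m·exp(0.125)
- observed-only mean = m·exp(0.125)·Φ(z − 0.5)/F

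Example, m = 48 h and c = 72 h: z = 0.811, F = 0.791, Φ⁻¹(0.396) = −0.265, and the observed-only median is 48·exp(−0.132) = 42.1 h.

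| True median (mean) | Rescue at | Uncleared | Observed-only median | Observed-only mean |
|---|---|---|---|---|
| 48 h (54.4 h) | 60 h | 32.8% | 38.8 h | 38.7 h |
| | 72 h | 20.9% | 42.1 h | 42.8 h |
| | 120 h | 3.3% | 47.0 h | 51.1 h |
| | 168 h | 0.6% | 47.8 h | 53.5 h |
| 36 h (40.8 h) | 60 h | 15.4% | 32.7 h | 33.7 h |
| | 72 h | 8.3% | 34.2 h | 36.1 h |
| | 120 h | 0.8% | 35.8 h | 40.0 h |
| 24 h (27.2 h) | 60 h | 3.3% | 23.5 h | 25.6 h |
| | 72 h | 1.4% | 23.8 h | 26.3 h |

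In every row c exceeds m. Keeping all patients and ranking the uncleared last therefore returns the true median exactly.

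**At the trial's size.** Take 10 patients with assumed times evenly spaced from 12 to 72 h, a step of 60/9 = 6.67 h. If the slowest two are rescued uncleared, the other eight run from 12 to 58.7 h, and their mean and median are both (12 + 58.7)/2 = 35.3 h. With all ten kept and the two ranked last, the median is (38.7 + 45.3)/2 = 42.0 h. A Kaplan-Meier routine that takes the next event time when the curve sits exactly at one half gives 45.3 h.

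**Recurrence to Day 42.** Suppose 3 of 10 patients recur and 2 are lost. The as-observed proportion is 3/8 = 37.5%. Kaplan-Meier gives between 3/10 = 30% (losses after all recurrences) and 37.5% (losses before any). Now suppose instead that 2 of 10 are rescued uncleared and 1 recurs. Recurrence among those who cleared is 1/8 = 12.5%, while 3/10 = 30% failed treatment. The result depends on a denominator that the SAP does not state.

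**The case against.** The strongest case against the point has five parts.

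1. **The SAP never says that rescued patients are excluded.** This is true. Exclusion is inferred from the observed-only rule. However, the only other way to put a number in is the post-rescue time, which errs in the same direction.

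2. **Rescue at 60 h for everyone is not the documents' rule.** This stands. Rescue from 60 or 72 h requires fever, and the window differs by species. The 60 h row is an extreme in which every slow patient is febrile and has *P. falciparum*. At the cut-offs that apply without fever, the median moves by about 1 h or less.

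3. **The cohort decisions do not depend on these times.** This stands. A reader might infer that the Cohort 2 question, whether cobicistat is needed, is distorted. The documents do not support that. Progression is decided by Day 14 crude ACPR and repeated drug-related SAEs, and crude ACPR already denies success to anyone who met a failure criterion earlier. The interim reviews look at parasite reduction, but no stated rule uses a clearance or fever time.

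4. **Recurrence is listed without being defined as a time, so a proportion is a fair reading.** This stands. A reader might also infer that dropping lost patients flatters the drug. In the example above the as-observed figure equals or exceeds Kaplan-Meier.

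5. **Other outputs show the missing patients.** Parasite-count figures, the listings and the 24/48/72 h summaries would let a reader find rescued patients among 10 per arm. That helps interpretation but does not correct the stated mean or median. The derivation tables and the full clinical protocol were not supplied and could hold a rule.

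**Conclusion.** The point holds for parasite clearance time, PC50/90/99/100 and fever clearance time. The stated summary has no place for a patient rescued uncleared, although such patients are foreseen. For those rescued because parasites persist, either available handling makes clearance look faster. Patients rescued early on clinical or platelet grounds need not be the slowest, so the direction is less certain for them.

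The size cannot be taken from the documents. Under the assumed lognormal times it runs from negligible (0.5 h or less on a true median of 24 h) to about 9 h on a true median of 48 h. The upper end requires rescue of all uncleared patients at 60 h. The mean is more sensitive than the median.

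The primary endpoint and the progression rules are untouched. No claim is made that the as-observed recurrence proportion favours the drug. For recurrence the fault is an unstated denominator and no rule for patients rescued before clearing. This is a cheap improvement to secondary, descriptive results in an exploratory study.

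**What to change.** In SAP section 4, Primary Analysis (Efficacy):

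- **Clearance times.** Replace means and medians for parasite clearance time, PC50/90/99/100 and fever clearance time with Kaplan-Meier or cumulative-incidence medians, by cohort and species, over all dosed patients. Treat rescue before clearance as a competing event: the patient stays in the set as not cleared to the end of a stated window, such as Day 7. Do not censor at the rescue time, because rescue is informative about clearance.
- **Rescues.** Report the number rescued uncleared beside each median.
- **Recurrence to Day 42.** State the denominator. Report patients rescued before clearing as treatment failures and not as recurrence-free. Censor only patients lost to follow-up.
- **Missing data.** Reconcile the no-imputation rule in section 4 with the multiple-imputation sentence in section 3, and say that neither is used to fill in a clearance time after rescue.

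The inputs are already planned as Listing 2 (parasite counts), Listing 4 (fever clearance) and Listing 8 (definitive antimalarial treatment), so no new data are needed. The cost is SAP wording and a little standard SAS code. The downside is that a median may be reported as not reached in a weak arm, which would be a correct description of that arm.
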